10.3 Successive sampling method

Successive sampling PSE method (SS-PSE) is based on data collected by the RDS methodology¹⁷. This method estimates the group size accounting for each participant's social network size, time and sequence of enrollment, number of people recruited by each participant. The underlying assumption is that the bigger network the respondent has, the earlier s/he will be recruited to the study. The recommended approach is to use the social network questions to impute a new degree (the number of people they know and have seen in the past two weeks who fulfill the study eligibility criteria) for each participant to reduce the recall bias. Prior knowledge about the population size, the imputed degree and other sampling data are used in a Bayesian framework (i.e., to quantify uncertainty about unknown quantities by relating them to known quantities) to quantify a population estimate with probability bounds. The SS-PSE will be conducted in "sspse" package for R or RDS-Analyst.

¹⁵ [Blue Book](#)

¹⁶ Wesson P, Lechtenberg R, Reingold A, McFarland W, Murgai N. Evaluating the Completeness of HIV Surveillance Using Capture-Recapture Models, Alameda County, California. AIDS and Behavior. 2018 Jul;22(7):2248-2257. DOI: 10.1007/s10461-017-1883-6.

¹⁷ Handcock MS, Gile KJ, Mar CM. Estimating the size of populations at high risk for HIV using respondent-driven sampling data. Biometrics. 2015;71(1):258–266

10.4 Calculation of the aggregated city-level estimates

10.4.1 Estimates validation

In order to validate the estimates obtained by all methods, the most probable range of PWID number in each IBBS city of survey will be determined:

- The coverage of PWID by prevention services provided by NGO (with a correction coefficient [see section 10.1] if applicable) will be used as a limiting minimum.
- Four percent of the total adult (age 15-59) general population as of January 1, 2023 (with appropriate correction for migration, if available) will be used as a limiting maximum. Previous rounds of estimations demonstrated that 3-4% threshold is adequate for the PWID group.

Estimates that are outside of the probable range will be excluded from further analysis.

10.4.2 Estimates triangulation

Several estimates, calculated at a local level, will represent an estimation range for the number of PWID. This allows to compare the validity of individual methods and to define the most probable range at a city level. The final estimate of the group size is determined by intersection of the maximum number of separate assessment ranges and by averaging. A PSE method called anchored multiplier, that allows synthesizing several population size estimates into a single consensus estimate, is also planned. Anchored Multiplier calculator¹⁸, uses a Bayesian simulation model to combine empirical estimates. The calculator is suitable for entering data into beta distribution, which reflects data "strength". "Stronger" data (with narrower confidence interval) will have greater impact on the final estimate than "weaker" data (with wider confidence interval). The single city-level consensus estimates will be considered final and will be used for further calculations.

¹⁸ <https://globalhealthsciences.ucsf.edu/resources/tools>

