4.4 Sample size and power calculation

To calculate the sample size, a design effect was empirically estimated in the 2020 IBBS data set using the Gile's SS estimator based on the actual network size in "RDS" package in R v.4.0.5 (Table).

	HIV prevalence				Viral suppression			
	Est.	95% CI LL	95% CI UL	D.Eff.	Est.	95% CI LL	95% CI UL	D.Eff.
Bila Tserkva	16.1%	10.2%	21.9%	3.11	77.7%	66.6%	88.7%	2.39
Dnipro	26.5%	19.8%	33.2%	2.78	68.8%	54.8%	82.6%	3.56
Ivano-Frankivsk	9.3%	5.8%	12.9%	2.61	89.3%	82.8%	96.4%	1.44
Kirovohrad	10.2%	7.0%	13.4%	1.80	74.2%	61.4%	87.3%	2.70

Kryvyi Rih	21.9%	16.1%	27.7%	2.13	70.6%	59.9%	81.1%	1.72
Kyiv	18.2%	12.9%	23.5%	3.27	86.0%	77.0%	95.0%	2.96
Mariupil	30.5%	25.3%	35.6%	2.11	80.9%	72.7%	89.1%	2.21
Mykolaiv	33.2%	27.5%	38.9%	2.88	76.4%	68.3%	84.4%	2.49
Odessa	21.2%	15.3%	27.1%	2.50	80.7%	73.4%	87.9%	1.31
Kharkiv	7.5%	4.1%	11.0%	2.12	90.9%	91.0%	91.0%	-
Khmelnytskyi	29.7%	23.7%	35.7%	2.47	81.9%	74.3%	89.3%	1.91
Cherkasy	38.4%	31.4%	45.6%	2.43	86.5%	80.1%	93.0%	1.61

As shown, the design effect for HIV prevalence ranges from 1.8 to 3.3, and for viral suppression from 1.3 to 3.6. Therefore, a conservative value of 3.0 is used for the following sample size calculation.

The calculation was made for *the single sentinel cluster* sample, with expected HIV prevalence of 21% and 44% viral suppression (combined weighted estimate using 2020 round data for 5 cities and 2017 data for Lviv). Based on the simple asymptotic CI formula,¹¹ 0.05 probability of type I error, anticipated 5% of missing data, and 14% desired precision level for the viral suppression indicator (e.g. 44±7%), the resulting sample size should be 2914.

[figure not shown]
In order to simplify trend analysis across rounds, the total sample will be distributed evenly across participating cities, yielding a rounded target sample size of 500 in each city. This result corresponds to the standard universal sample size used in the US NHBS-IDU.¹² At the city level, assuming the design effect of 3.0 and 5% of missing data (e.g. incomplete data entry, entry errors), a sample size of 500 will provide ~16% precision for a maximally-conservative estimated prevalence for any indicator – 50% (i.e. 50±8%, the interval will be narrower for proportions closer to extremes, either 0 or 100%).

The same target sample size will be used for each additional city (outside the sentinel cluster).

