10.1 Multiplier method

The multiplier method is based on availability of at least two overlapping data sources specific to the population of interest, one being a count or registry of unique individuals belonging to the population, and another one being a representative survey that assessed whether the participants are present in the first data source. The data sources have to be independent of each other; define the target group in the same way; present the same time period, age and target group geography; be of sufficient data quality.

The formula to calculate the population size using the multiplier method is: $N = M/P$, Where:

N = Estimated Size

P = Proportion of survey participants who reported belonging to the registry (receiving the service, the object, or participating in the survey).

M = Number of individuals in the registry.

The 95% confidence intervals for proportions calculated for descriptive statistics using bootstrapping method with RDS weights will be used to calculate the lower- and upper limits for the population estimates.

The following data sources and indicators will be used for the multiplier method:

#	PSE indicator	Questionnaire item	Existing registry	Data provider
1	Registration in drug treatment clinics	Are you registered with the state narcological clinic in connection with drugs abuse or addiction?	Currently undetermined. Previously: Reporting form No.11 "Report on the morbidity of individuals with mental and behavioral disorders due to psychoactive substance use", annual. Table 2120 "Number of individuals with mental disorders due to intravenous drug use". Indicator: "among people under the supervision at the end of the reporting period".	Regional and city state drug treatment clinics.

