5	Harm reduction coverage	Are you a client of any NGO working with people who inject drugs (have a client's card or an individual code)? Have you received free sterile needles/syringes from a non-governmental organization within the last 12 months (March 2022-March 2023)? Have you received free condoms from a non-governmental organization within the last 12 months (March 2022-March 2023)? Have you received HIV testing services from a non-governmental organization within the last 12 months (March 2022-March 2023)?	Number of PWID who received any harm reduction services in March 2022-March 2023.	SYREX database
6	Needle and syringe program coverage	Have you received sterile needles/syringes from a non-governmental organization within the last 3 months (January-March 2023)?	Number of PWID who have received syringes/needles within NGO network (average indicator for 3 months).	SYREX database
7	Condom programming coverage	Have you received condoms from a non-governmental organization within the last 3 months (January-March 2023)?	Number of PWID who have received condoms within NGO network (average indicator for 3 months).	SYREX database
8	HIV testing coverage	Were you tested with a rapid test for HIV in non-governmental organization in 2022? Were you tested with a rapid test for HIV in non-governmental organization in 2023 (January-March)?	Number of PWID who have been tested with the HIV rapid tests for 2022 and 2023 (separately for each year).	SYREX database
9	HCV testing	Did you get a rapid test for hepatitis C at NGO	Number of PWID who have been tested with the HCV	SYREX

	coverage	in 2022? Did you get a rapid test for hepatitis C at NGO in 2023 (January-March)?	rapid tests for 2022 and 2023 (separately for each year).	database
10	HBV testing coverage	Did you get a rapid test for hepatitis B at NGO in 2022? Did you get a rapid test for hepatitis B at NGO in 2023 (January-March)?	Number of PWID who have been tested with the HBV rapid tests for 2022 and 2023 (separately for each year).	SYREX database
11	Syphilis testing coverage	Did you get a rapid test for syphilis at NGO in 2022? Did you get a rapid test for syphilis at NGO in 2023 (January-March)?	Number of PWID who have been tested with the syphilis rapid tests for 2022 and 2023 (separately for each year).	SYREX database

These data will be collected for both IBBS and non-IBBS regions, to enable extrapolation of estimates.

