Variance will be calculated by using the following formula:

$$Var(N) = \frac{(S_1 * S_2 * (S_1 - R) * (S_2 - R))}{R^3}$$

95% confidence interval will be calculated by using the following formula:

$$95\% CI: N \pm 1.96 * \sqrt{Var(N)}$$

For the 2023 PSE round will use two different unique objects to improve accuracy of the method. During the formative assessment, the Regional Working Group, will prepare a list – as exhaustive as possible – of the venues where PWID can be found. On a specified date, approximately two weeks prior to the start of IBBS data collection, designated representatives of the regional working groups will visit **all** venues and distribute the first unique object to the PWID present at the venue and who meet eligibility criteria (same as for IBBS, Annex 8). Results of distribution will be recorded in the Form (Annex 36. Unique Object Distribution Form). One week after that, a second visit to **all** venues will be done to distribute the second object, results will also be recorded in the Form. If it will not be feasible to visit all locations within the limited time frame, the venues for each visit will be selected randomly and independently (no overlap is required), to ensure that samples are independent. According to the guidelines¹⁵, the number of unique objects should be at least twice that of the target sample size. Since the sample size in each city will be equal to 500, the number of unique objects of each type to be distributed is 1000, total 2000 per city, or 4,000 in two cities. The cities will be selected by the National Working Group.

The following log-linear regression model will be used to estimate population size based on three 'captures'¹⁶.

$$\log E(Z_{ijk}) = u + u1I(i = 1) + u2I(j = 1) + u3I(k = 1) + u12I(i = j = 1)$$

The model estimates the log expected count of the population size for a 3-list capture-recapture analysis and adjusts for a positive (or negative) dependency between lists i and j. This model allows to relax the assumption of independency between captures by controlling for list dependencies through interaction terms.

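### The consensus city size makes no allowance for dependence between multipliers, although seven of the eleven use one NGO database and the same respondents

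*Protocol*

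**What the plan says.** Section 10.1 introduces its table with "The following data sources and indicators will be used for the multiplier method" and lists eleven indicators. In each, a registry count M is divided by P, the share of survey participants who report being in that registry. The limits of each size estimate come from the RDS-weighted bootstrap interval for P, so M is treated as known.

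Rows 5-11 name SYREX, the NGO service database, as the source of M. Row 5 is the broad count ("Number of PWID who received any harm reduction services in March 2022-March 2023"), set against four questionnaire items. Rows 6-7 are syringes and condoms over three months. Rows 8-11 are HIV, HCV, HBV and syphilis tests, counted separately for 2022 and 2023. Rows 1-4 cover narcology registration, substance use treatment, police detention and MOUD; the registries for rows 1-2 are still undetermined.

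Section 10.4.1 sets a plausible range whose floor is NGO service coverage, then states "Estimates that are outside of the probable range will be excluded from further analysis". Section 10.4.2 describes overlapping ranges and averaging, and adds the anchored multiplier, "that allows synthesizing several population size estimates into a single consensus estimate, is also planned", in which a narrower interval means more influence. The consensus is final and goes into later calculations.

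The one adjustment for dependence is the interaction term in the section 10.2 log-linear model. It concerns the three captures, with unique objects handed out in two cities. Nothing similar covers the multipliers.

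**The concern.** Weighting by interval width is sound when inputs err independently. The SYREX multipliers do not: the same respondents supply every P, the services overlap heavily, and the counts come from one client register. If a city's sample happens to hold too many NGO clients, every SYREX estimate falls together, and adding rows cannot average this out. The link is plausible: section 14.4 has seeds recruited by NGO representatives, although section 6.3 requires at least one seed who is not a client. Double-counted clients, a risk that section 10.1 itself raises, would likewise tend to push the SYREX counts up together.

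Two things are at stake. The published interval for city size would look more certain than the data allow. The point estimate would also lean on one source because that source is listed many times. City sizes are used as weights in sections 9.2 and 9.4, and the latest available size gives the number of PWID living with HIV in section 9.6.

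**Working it through.** **Inputs from the protocol.** Section 10.2: "Since the sample size in each city will be equal to 500". Section 4.4, city level: "assuming the design effect of 3.0 and 5% of missing data". Section 4.4, error rate: "0.05 probability of type I error, anticipated 5% of missing data", hence z = 1.96. Section 2.0: NGO coverage about 60%; MOUD coverage about 7% of people who inject opioids. **Not in the protocol, so assumed:** the correlation between multipliers, most values of P, and inverse-variance pooling as a stand-in for the calculator.

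**1. Reproduce the stated city precision.** n = 500 × 0.95 = 475. Half-width = 1.96 × √(3 × 0.25 / 475) = 0.078; full width 0.156. This matches the stated precision of about 16% (50±8%). Effective n = 475 / 3 = 158.

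**2. Count the inputs.** SYREX supplies rows 5-11: 7 of 11 indicators = 64%. Split by year, rows 5-7 give 3 and rows 8-11 give 4 × 2 = 8, so 11 estimates.

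**3. Understatement of the standard error.** For k equally precise estimates with common correlation ρ, true SE / stated SE = √(1 + (k − 1)ρ).

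| ρ (assumed) | k = 7 | k = 11 |
|---|---|---|
| 0.1 | 1.26 | 1.41 |
| 0.3 | 1.67 | 2.00 |
| 0.5 | 2.00 | 2.45 |

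For example, k = 11 and ρ = 0.5: √(1 + 10 × 0.5) = √6 = 2.45. Coverage of a nominal 95% interval is 2Φ(1.96 / ratio) − 1: 83% at a ratio of 1.41, 67% at 2.00, 58% at 2.45.

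**4. Mixed pool.** Take 13 inputs: 7 SYREX, 4 other multipliers and 2 from earlier IBBS rounds. With correlation 0.2-0.9 within SYREX and 0.05-0.2 elsewhere, the ratio is about 1.4-2.5.

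**5. Simulation.** Seven correlated NGO indicators (P from 0.2 to 0.6) in one sample of 158, with mean pairwise correlation of the indicators 0.18 to 0.54: ratio 1.41 to 1.97, coverage 83% down to 68%.

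**6. NGO share of weight.** The relative SE of M/P is √((1 − P) / (P × 158)). At P = 0.60 it is 6.5%; at P = 0.07 it is 29%. The weight ratio is (0.29 / 0.065)² ≈ 20. Weight is proportional to P / (1 − P), so for the 13 inputs:
- all P equal: 7 / 13 = 54%;
- low NGO proportions (SYREX 0.3, 0.3, 0.2, 0.2, 0.15, 0.1, 0.1; other multipliers 0.3, 0.2, 0.2, 0.07; earlier IBBS 0.1, 0.1): 59%;
- proportions led by the section 2.0 levels (SYREX 0.6, 0.6, 0.4, 0.4, 0.3, 0.2, 0.2; other multipliers 0.15, 0.1, 0.1, 0.07; earlier IBBS 0.1, 0.1): 88%.

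SS-PSE and the unique-object estimates are left out here; adding them would lower these shares somewhat.

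**The case against.** The strongest reply is that the protocol says several estimates, not all of them. It examines service indicators for consistency first (section 10.1) and drops implausible values (section 10.4.1), and the final input list may sit in an analysis plan that is not shown. The calculator is described as a Bayesian simulation using beta distributions, and its treatment of overlapping inputs is unknown. This stands as a limit on the numbers. It does not remove the point: the protocol fixes the indicator list, the weighting principle and the finality of the result, and neither screen deals with correlation.

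A reader might go further in several ways that the documents do not support:
- **That the interval is twice too narrow, or has a known coverage.** Those figures need an assumed correlation and a stand-in for the calculator. The protocol states no consensus interval.
- **That the protocol declares the multipliers independent.** Section 10.1 says "The data sources have to be independent of each other", but this concerns registry against survey within one multiplier. Independence between multipliers is inferred from the lack of any adjustment.
- **That rows 6-11 are strict parts of row 5.** Rows 8-11 include January-February 2022, outside row 5's window, and rows 6-7 use three-month averages. The overlap is large but not exact.
- **That NGO data prevail whatever the other sources show.** Rows 1-4 could also be split: row 1 once, row 2 up to four ways, row 3 up to six, row 4 twice, or 13 in all. SYREX would then be 11 of 24 multiplier estimates, 46% by count, although those extra estimates would be correlated too.
- **That the narrow interval passes into later results.** Sections 9.2, 9.4 and 9.6 use the size itself; none is said to carry its interval.

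**Conclusion.** The structural point holds. Seven of eleven multipliers share a register and all share respondents, and section 10.4.2 combines inputs by interval width with no term for dependence. If the SYREX multipliers enter as separate inputs, the consensus interval is too narrow and NGO data carry most of the weight in the illustrated cases.

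The size is illustrative: an SE understated about 1.4- to 2.5-fold for assumed correlations of 0.1 to 0.5 among 11 estimates, 2.0-fold for 7 at 0.5, and an NGO weight share of 54-88% depending on assumed proportions. A factor of two is mid-range, not an established result. The direction needs only positive correlation, which shared respondents and overlapping services make very likely. The change should be made, since it is nearly free.

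**What to change.** In section 10.4.2, state that only one SYREX-based estimate per city enters the anchored multiplier. It can be one indicator fixed before the data are seen, or the median of the SYREX estimates with the interval of a single one, not narrowed for their number. Likewise enter one estimate per other registry (narcology, police, MOUD). Report the remaining SYREX multipliers as a within-source consistency check.

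Add two statements. First, the remaining inputs still rest on the same respondents, so some correlation persists; resampling respondents jointly across all indicators would let the pooling carry it. Second, one input per source does not remove bias from over- or under-recruiting NGO clients, since a single SYREX estimate would be off by as much. For that reason, report the consensus with and without SYREX as a sensitivity check.

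The cost is wording and fewer calculator inputs, with no new data. The downside is a wider interval for city size.

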11.0 DATA MANAGEMENT PLAN

Data Management Plan identifies the resources and tools needed for data collection, storage, and usage, providing for effective planning of data input, clearing and analyzing, control the data quality, managing data usage and exchange, ongoing management and data documentation. The plan covers three databases - survey data, laboratory data, RDS-coupons management base.

The Data Management Plan provides a number of components, namely: data documentation, data dictionary, unique participant's ID, data access, data security.

All IBBS personnel will be trained on the procedures of protecting confidentiality of participants within the training framework and will sign the Data Use and Confidentiality Agreement which explains the procedures for dealing with confidential data and liability for violations (Annex 27. Data Use and Confidentiality Agreement for personnel).

11.1 Data documentation

The following forms and tools will be used:

1. Verbal informed consent to be interviewed;
2. Formative Assessment Protocol;
3. Log of compensation to the key informants;
4. Verbal consent to questionnaire piloting;
5. Log of compensation to the respondents for questionnaire piloting;
6. Introduction for the potential participants of the survey;
7. Screening questionnaire for primary respondents;
8. Screening Form for PWID;
9. Survey participant's coupon;
10. Participant's Checklist;
11. Participant's Informed Consent (Ukrainian version);
12. Participant's Informed Consent (Russian version);
13. Registration form for refusal to participate in the survey;
14. Questionnaire of refusal to participate in the survey for recruiters;
15. Test Results Form;
16. Referral form for the survey participant;
17. Certificate of HIV test results;
18. Certificate of test results for anti-hepatitis C, syphilis;
19. Social support referral form for the survey participant;
20. Registration log for referrals to HIV clinic;
21. Registration log of referrals to healthcare facilities;
22. Form of rejected DBS registration;
23. DBS registration form;
24. Form of routine forwarding of the DBS samples to the Reference Laboratory;
25. Compensation Log;
26. Instructions for a recruiter;
27. Data Use and Confidentiality Agreement for personnel;
28. Unforeseen circumstances notification form;

29. Reporting form on serious adverse events;
30. Form of the Protocol deviations;
31. Weekly reporting form of the national coordinator;
32. Weekly reporting form of the regional coordinator;
33. Report of the regional team on the survey findings;
34. Report on the monitoring visit to the survey site;
35. Fact sheet on understanding recent and long-term HIV infection
36. Survey Participant's Questionnaire.
37. Verbal consent to Unique object

All forms are linked with the participant's ID and do not contain the participants' identifying information. The regional coordinator collects all completed forms from the responsible RDCT member (coupon manager, interviewer, healthcare worker). The regional coordinator checks the completeness and correctness of forms data, cross-checks the number of records between forms. On a monthly basis, a regional coordinator sends paper copies of the forms in a sealed envelope by a courier service to the national coordinator. Before that, the form copies are stored in his/her office in a locked cabinet.

